#### Commercially Confidential Information

Descriptive statistics (unless otherwise specified) on continuous data will include number of non-missing observations (n) mean (arithmetic), standard deviation (SD), median, Q1 (25th percentile), Q3 (75th percentile), minimum and maximum, while for categorical variables frequencies and percentages will be reported.

Graphical presentations of individual and summary data will be provided, as applicable.

- Inferential modelling for primary and key secondary variables will include
- stratification factor baseline ESSDAI score  $<10$  or  $\geq 10$ . The stratification factor baseline ESSDAI score will be based on the data in the database and not on the IRT data.

If not otherwise specified, p-values will be presented as two-sided p-values and two-sided confidence intervals will be displayed.

#### 2.1.1 General definitions

The term '*study treatment*' or '*study drug*' refers to the Novartis investigational drug, LOU064 or placebo, dispensed by the investigators during the study. Specifically, the following grouping scheme will be used for reporting of summaries:

Placebo

LOU064 100 mg *qd*

LOU064 100 mg *bid*

Any LOU064 (i.e. LOU064 100 mg *qd* and 100 mg *bid* combined)

The term '*date of first administration of study drug/treatment*' refers to the date on which the study drug/treatment was given for the first time in the CLOU064E12201 study.

The term '*date of last administration of study drug/treatment*' refers to the date on which the study drug/treatment was given for the last time in the CLOU064E12201 study.

The term '*study day*' refers to the Analysis Relative Day, Relative Start Day or Relative End Day, as applicable. Day 1 is defined as the date of first dose of study drug (LOU064 or placebo). Study day is defined as the number of days since the date of first dose of study treatment (Day 1).

Therefore, for a particular date, study day will be calculated as follows:

- for dates on or after the first administration of study treatment,  
Study day = Assessment date – Date of first dose of study treatment +1
- for dates prior to the date of first administration of study treatment,  
Study day = Assessment date – Date of first dose of study treatment.

The term '**baseline**' refers to the last assessment performed prior to administration of the first dose of study treatment. In case the scheduled baseline assessment value is missing, the screening value if available will be used instead.

The term '**treatment-emergent adverse event**' refers to any adverse event (AE) started after the first dose of study treatment, or events present prior to the first dose of study treatment but increased in severity (based on preferred term (PT)).

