6.2.3 Rescue medication

There is no established, approved immunosuppressive treatment for SjS. Patients may receive nonsteroidal anti-inflammatory drugs (NSAIDs), paracetamol, or symptomatic care at the discretion of the treating physician as outlined in [Section 6.2.1](#). Each concomitant drug must be individually assessed against all exclusion criteria and prohibited medication ([Table 6-3](#)). When in doubt the investigator should contact the Novartis medical monitor before randomizing a patient or allowing a new medication to be started. If any of the medications listed in [Table 6-3](#) is deemed a necessary rescue therapy, the investigator must follow the actions to be taken outlined in this table. Any potential rescue medication is to be provided by the study center or personal physician. Patients should be encouraged to come for the end-of-study visit even when discontinued permanently from study medication.

There is no specific rescue medication for LOU064. LOU064 is eliminated within a few hours from the body and no specific antidote is necessary. Pharmacodynamic activity of LOU064 may take longer as the elimination time because of the covalent binding to the BTK-molecule. However, any direct immunosuppressive activity is not expected to take more than a few days.

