9.1 Discontinuation and completion

9.1.1 Study treatment discontinuation and study discontinuation

Discontinuation of study treatment for a subject occurs when study treatment is stopped earlier than the protocol planned duration and can be initiated by either the subject or the investigator.

The investigator must discontinue study treatment for a given subject if he/she believes that continuation would negatively impact the subject's well-being.

Study treatment must be discontinued under the following circumstances:

- Subject's decision
- Pregnancy

- Use of prohibited treatment as per recommendations in the prohibited treatment section ([Section 6.2.2](#))
- Any situation in which study participation might result in a safety risk to the subject, e.g. required surgical interventions associated with a risk of clinically significant bleeding
- Following emergency unblinding
- Emergence of the following AEs:
 - AEs including severe or serious hypersensitivity reactions for which continued exposure to the study drug would be detrimental
 - Abnormal liver laboratory results requiring discontinuation (see [Section 16.2](#))
 - Abnormal renal laboratory results requiring discontinuation (see [Section 16.3](#))
 - Platelets < 75 000/mm³
 - Any other laboratory abnormalities that in the judgment of the investigator, taking into consideration the subject's overall status, prevents the subject from continuing participation in the study
 - Patient received a live virus vaccination during the study

If discontinuation of study treatment occurs, the investigator should make a reasonable effort to understand the primary reason for the subject's premature discontinuation of study treatment and record this information.

Subjects who discontinue study treatment or who decide they do not wish to participate in the study further should NOT be considered withdrawn from the study UNLESS they withdraw their consent (see [Section 9.1.2](#)). **Where possible, they should return for the assessments** indicated in the assessment schedule ([Table 8-1](#)). If they fail to return for these assessments for unknown reasons, every effort (e.g. telephone, e-mail, letter) should be made to contact the subject/pre-designated contact as specified in the lost to follow-up section ([Section 9.1.3](#)). This contact should preferably be done according to the study visit schedule ([Table 8-1](#)).

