If the subject cannot or is unwilling to attend any visit(s), the site staff should maintain regular telephone contact with the subject, or with a person pre-designated by the subject. This telephone contact should preferably be done according to the study visit schedule.

After study treatment discontinuation, at a minimum, in abbreviated visits, the following data should be collected at clinic visits or via telephone/email contact:

- New / concomitant treatments
- Adverse Events / Serious Adverse Events

The investigator must also contact the IRT to register the subject's discontinuation from study treatment.

If discontinuation occurs because treatment code has been broken, please refer to Emergency breaking of treatment code section (see [Section 6.6.3](#)).

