- Dose not changed
- Dose Reduced/increased

- Drug interrupted/withdrawn
6. Its outcome i.e., its recovery status or whether it was fatal

Conditions that were already present at the time of informed consent should be recorded in medical history of the subject.

AEs (including lab abnormalities that constitute AEs) should be described using a diagnosis whenever possible, rather than individual underlying signs and symptoms.

AE monitoring should be continued for at least 30 days following the last dose of study treatment.

Once an adverse event is detected, it must be followed until its resolution or until it is judged to be permanent (e.g. continuing at the end of the study), and assessment must be made at each visit (or more frequently, if necessary) of any changes in severity, the suspected relationship to the interventions required to treat it, and the outcome.

Information about adverse drug reactions for the investigational drug can be found in the Investigator's Brochure (IB).

Abnormal laboratory values or test results constitute adverse events only if they fulfill at least one of the following criteria:

- they induce clinical signs or symptoms
- they are considered clinically significant
- they require therapy

Clinically significant abnormal laboratory values or test results must be identified through a review of values outside of normal ranges/clinically notable ranges, significant changes from baseline or the previous visit, or values which are considered to be non-typical in subjects with the underlying disease. See [Section 16.1](#), [Section 16.2](#) and [Section 16.3](#) for alert ranges for laboratory and other test abnormalities.

Follow the instructions found in the Site Operations Manual for data capture methodology regarding AE collection for subjects that fail screening.

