12.5.2 Safety endpoints

All safety endpoints (i.e. AEs, laboratory data, vital signs, and ECG) will be summarized by treatment for all subjects in the safety set.

Adverse events

All information obtained on AEs will be displayed by treatment group and subject.

The number (and percentage) of subjects with treatment emergent AEs (events started after the first dose of study medication or events present prior to start of double-blind treatment but increased in severity based on preferred term) will be summarized in the following ways:

- by treatment, primary system organ class and preferred term.
- by treatment, primary system organ class, preferred term and maximum severity.
- by treatment, Standardized MedDRA Query (SMQ) and preferred term.

Separate summaries will be provided for study medication related AEs, deaths, serious adverse events, and other significant AEs leading to discontinuation. A subject with multiple AEs within a primary system organ class is only counted once towards the total of the primary system organ class.

Laboratory data

The summary of laboratory evaluations will be presented for four groups of laboratory tests (hematology, serum chemistry, urinalysis and coagulation). Descriptive summary statistics for the change from baseline to each study visit will be presented. These descriptive summaries will be presented by test group, laboratory test and treatment group. Change from baseline will only be summarized for subjects with both baseline and post baseline values.

Vital signs

Analysis of the vital sign measurements using summary statistics for the change from baseline for each post-baseline visit will be performed. These descriptive summaries will be presented by vital sign, treatment group and visit/time. Change from baseline will only be summarized for subjects with both baseline and post-baseline values. Shifts with respect to normal ranges and number and percentage of notable abnormalities will also be summarized.

ECG

Summary statistics will be provided by treatment and visit/time.

PR, QRS, QT, QTcF, and RR intervals will be obtained from 12-lead ECGs for each subject during the study. Frequency tables will be produced for the number and percentage of subjects with notable QT and QTcF intervals and with noteworthy PR, QRS and Heart Rate interval or changes from baseline.

Commercially Confidential Information

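### The treatment-emergent AE definition has a start but no cut-off after last dose, so late off-drug events of early discontinuers are tabulated as treatment-emergent

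*SAP*

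**What the plan says.** **Definition.** Under SAP 2.1.1 a TEAE "refers to any adverse event (AE) started after the first dose of study treatment", or is an earlier event that became more severe. Protocol 12.5.2 says the same: "events started after the first dose of study medication or events present prior to start of double-blind treatment but increased in severity". Neither refers to the last dose, although SAP 2.1.1 defines the date of last administration a few lines earlier. The endpoint tables (Protocol Table 2-1, SAP 1.2) limit TEAEs only to those occurring during the study.

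**Follow-up after stopping drug.** Protocol 9.1.1 says that subjects who stop treatment "should NOT be considered withdrawn from the study UNLESS they withdraw their consent". It adds: "Where possible, they should return for the assessments" of Table 8-1. AEs/SAEs and new or concomitant treatments are the minimum data: "After study treatment discontinuation, at a minimum, in abbreviated visits, the following data should be collected". Table 8-1 puts the End of Study (EOS) visit at Day 199, and a footnote makes it mandatory for early discontinuers too.

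**The 30-day interval.** Protocol 10.1.1 sets a floor: "AE monitoring should be continued for at least 30 days following the last dose of study treatment". Protocol 10.1.3 uses 30 days to limit SAE reporting to the sponsor's safety group. Protocol section 3 plans a 30-day drug-free follow-up before EOS.

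**Persistence of effect.** Protocol 6.2.3 states that the drug is eliminated within hours and that "any direct immunosuppressive activity is not expected to take more than a few days".

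**Summaries.** AE tables count subjects in the Safety Set, analysed by treatment received (Protocol 12.1 and 12.5.2, SAP 2.2 and 2.8.1). Exposure in SAP 2.4.1 ends at the end-of-treatment date.

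**The concern.** For a completer, the whole-study window and a last-dose-plus-30-days window coincide. For an early discontinuer they can differ by months, and events in the gap, possibly arising on newly started therapy, enter the same TEAE tables as events on drug.

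Safety and tolerability is a stated secondary objective. Protocol 9.1.1 requires treatment to stop for low platelets and for certain liver and renal abnormalities, so the amount of off-drug time could differ between LOU064 and placebo for reasons tied to the safety outcomes. The visible summaries are numbers and percentages of subjects with no exposure adjustment, so a reader of the tables could not separate on-drug from off-drug events. Because exposure stops at end of treatment, the exposure and TEAE tables also cover different periods.

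**Working it through.** **1. The plan's own timeline.** Six weeks of screening plus EOS at Week 29 gives 6 + 29 = 35 weeks, matching the stated maximum duration. Week 24 is Day 169, and 169 + 30 = 199, the EOS day in Table 8-1. A completer on schedule therefore has exactly 30 drug-free days.

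**2. One discontinuer followed to Day 199.** With last dose on Day L, off-drug days in the TEAE window = 199 − L, and days beyond last dose + 30 = 199 − (L + 30) = 169 − L.

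| Last dose | L | Off-drug days | Days beyond last dose + 30 | Share of 199 days |
|---|---|---|---|---|
| Week 4 | 29 | 170 | 140 | 70% |
| Week 8 | 57 | 142 | 112 | 56% |
| Week 12 | 85 | 114 | 84 | 42% |
| Week 16 | 113 | 86 | 56 | 28% |
| Week 20 | 141 | 58 | 28 | 14% |
| Week 24 | 169 | 30 | 0 | 0% |

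**3. Share of an arm's AE window.** The visible text gives no discontinuation rate. Assume a proportion d stops at times spread evenly over Days 1 to 169 and all are followed to Day 199. The mean excess per discontinuer is (168 + 0)/2 = 84 days, so the arm's share is d × 84/199:

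- d = 10%: 0.10 × 84/199 = 4.2%
- d = 25%: 0.25 × 84/199 = 10.6%

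**4. Effect on subject counts.** The tables count subjects, so person-time share is not the final measure. Assume a constant AE rate r per year. For last dose on Day L, the added probability of at least one TEAE under the whole-study window is

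exp(−r(L + 30)/365.25) − exp(−r × 199/365.25).

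Average this over L = 1 to 169 and multiply by 24d, where 24 is the expected group size in SAP 1.1.

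| r per year | Mean added probability per discontinuer | Extra subjects, d = 10% | Extra subjects, d = 25% |
|---|---|---|---|
| 0.5 | 0.095 | 0.23 | 0.57 |
| 1 | 0.157 | 0.38 | 0.94 |
| 2 | 0.216 | 0.52 | 1.29 |
| 4 | 0.213 | 0.51 | 1.28 |

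The range is about 0.2 to 1.3 subjects per arm of 24. One subject is 1/24 = 4.2 percentage points, so 1.3 subjects is about 5.4 points.

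**5. The other reading of EOS.** Protocol section 3 and SAP 1.1 describe, for each individual subject, a follow-up of (about) 30 days after last administration before EOS. If EOS moves with an early last dose, AE collection ends near L + 30 and every excess above falls to about zero. Protocol 9.1.1 and Table 8-1 point instead to the full schedule. The figures in steps 2 to 4 are therefore upper limits.

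**The case against.** The strongest reply is that the plan does have a window, namely the whole study. The endpoint wording, Protocol 12.5.2 and SAP 2.1.1 agree on it, and it matches the primary efficacy analysis, which uses data regardless of treatment interruption. It also keeps observation time comparable between arms. A last-dose-plus-30-days cut-off shortens observation in the arm with more stopping, and so brings its own imbalance. **This stands**, and is why the whole-study count should be kept rather than replaced.

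The size is also limited. Return visits are only where possible, withdrawal of consent ends collection (9.1.2), emergency-unblinded subjects are withdrawn (6.6.3), and users of prohibited medication may be withdrawn case by case (Table 6-3). The safety summaries are descriptive, related TEAEs are tabulated separately, and all AEs are displayed by subject. These points stand and make the figures maxima. They do not make the main table distinguish on-drug from off-drug events.

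Finally, part of SAP 2.8.1 and the whole SAP appendix are redacted, so an end rule could exist there. No visible text refers to one, and the definition in SAP 2.1.1 is itself a complete sentence.

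A reader might infer that TEAEs have no end at all, or that the 30-day statements already supply one. Neither is supported. The study period bounds the events, while the 30-day statements set a minimum for monitoring, a limit on SAE reporting and a follow-up period, not a limit on TEAE status.

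**Conclusion.** The point holds as a modest, inexpensive improvement. The visible rule labels every AE that starts or worsens after first dose, at any time in the study, as treatment-emergent for the treatment received, including events long after drug activity is expected to have gone.

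At most, 140, 112 and 84 days of such time lie beyond last dose + 30 days for a last dose at Week 4, 8 and 12. At arm level the ceiling is about 4–11% of the AE window, or 0.2–1.3 extra subjects with any AE per arm of 24. This rests on follow-up to Day 199, 10–25% discontinuation at evenly spread times, complete follow-up, and constant rates of 0.5–4 AEs per year; the discontinuation and AE rates are assumptions.

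A reader might infer that the safety comparison is materially distorted. The documents do not show that: there is no visible discontinuation rate and no evidence that stopping would differ by arm, and on the other reading of EOS timing the excess nearly vanishes. Nor are events attributed to the assigned regimen, since the Safety Set uses treatment received.

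**What to change.** - **SAP 2.1.1:** define the TEAE period for the main tables as first dose to last dose + 30 days, using the date of last administration already defined there. Thirty days is the documents' own follow-up interval.
- **SAP 2.8.1:** tabulate later events separately as post-treatment, and also present the whole-study count so that observation time stays comparable between arms.
- **SAP 2.8.3 and 2.8.4:** apply the same period to treatment-emergent laboratory, vital-sign and ECG abnormalities, unless the redacted appendix already sets one.
- **EOS timing:** reconcile Protocol section 3 and SAP 1.1 (EOS about 30 days after last administration) with Protocol 9.1.1 and Table 8-1 (discontinuers stay on the schedule, EOS at Day 199). The resolution is for the sponsor.

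The cost is a sentence, a date filter and one extra set of AE tables. No safety data are lost, and results for completers followed on schedule are unchanged.

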### Visit windowing

For the efficacy analysis, when visit windows are used, all visits will be re-aligned, i.e. they will be mapped into one of the visit windows. For example, if the Week 4 visit of a subject is delayed and occurs on Day 46 in stead of Day 29, it will be re-aligned to visit window Week 8. In the case of major deviations from the visit schedule, or due to unscheduled visits, several assessments of a subject may fall in a particular visit window (either scheduled or unscheduled). The rules to derive the visit windows are given in the Appendix.

## 2.2 Analysis sets

The following analysis sets will be used in this trial:

**Full Analysis Set (FAS):** will include all randomized subjects, except those who were mis-randomized. Mis-randomized subjects are defined as those subjects who were mistakenly randomized into the IRT prior to the site confirming all eligibility criteria had been met and to whom no study medication was given. Mis-randomized subjects are treated as screen failures.

Following to the intent-to-treat principle, subjects will be analyzed according to the treatment assigned at randomization, but actual stratum.

**Safety Set (SS):** includes all subjects who received at least one dose of study drug. Subject will be analyzed according to treatment received and the stratum they actually belong to in case of misallocation of strata during the randomization process. The safety set will be used in the analysis of all safety variables.

**PK Analysis Set:** includes all subjects with at least one available valid (i.e. not flagged for exclusion) PK concentration measurement, who received any study drug and with no protocol deviations that impact on PK data.

### **2.2.1 Subgroup of interest**

Subgroups of interest are listed below. These will not necessarily be applied to all analyses but used as specified in the protocol or this SAP.

- stratification factor baseline ESSDAI score  $<10$  or  $\geq 10$

### **2.3 Patient disposition, demographics and other baseline characteristics**

The FAS analysis set will be used for the analyses below.

#### **2.3.1 Patient disposition**

The subject disposition will be summarized by treatment group and overall and listed by treatment group and subject.

The number and percent of subjects screened, randomized, completed and discontinued from the study will be summarized with reasons for discontinuation.

#### **2.3.2 Demographics and other baseline characteristics**

Demographic (gender, age, race, ethnicity, weight, height, BMI and disease duration) and other baseline characteristics (ESSDAI and number of subjects per ESSDAI stratum (the actual stratum), ESSPRI, PhGA, EQ-5D, FACIT-F, unstimulated salivary flow, CCI use of DMARDs (split by type), and percentage of subjects with history of prior biologics treatment use) will be summarized descriptively for all subjects and by treatment group.

Relevant medical history, current medical conditions, results of laboratory screens, drug tests and any other relevant information will be listed by treatment group and subject.

#### **2.3.3 Protocol deviations**

Protocol deviations will be summarized by treatment group by protocol deviation category and protocol deviation term.

### **2.4 Treatments (study treatment, rescue medication, concomitant therapies, compliance)**

The safety analysis set will be used for the analyses below.

#### **2.4.1 Study treatment / compliance**

The duration of exposure to study treatment will be summarized by treatment group. In addition, the number of patients with exposure of at least certain thresholds (e.g. any exposure,  $0 - <1$ ,  $\geq 1 - <2$ ,  $\geq 2 - 4$ , etc ) will be displayed.

Duration of exposure of a treatment is defined as following:

Duration of exposure (days) = end of treatment date – date of first dose + 1

Duration of exposure (weeks) = duration of exposure (days)/7

